Safety data will be obtained at each of the two study visits from the spontaneous reports by patients of adverse events, vital sign monitoring, and focused physical examinations.

[name] should be contacted directly at this number to report medical concerns or questions regarding safety.

[contact]

b. Data safety monitoring

All safety data will be reviewed by the PI ([name] [name]).

c. Discontinuation criteria for individual subjects

Discontinued subjects are those who are enrolled in the study and for whom study treatment is terminated prematurely for any reason.

The subject is free to withdraw from the study treatment and/or study for any reason and at any time without giving reason for doing so and without penalty or prejudice. The investigator is also free to terminate a subject's involvement in the study at any time if the subject's clinical condition warrants it.

Subjects will be discontinued if:

- Subject experiences a serious or intolerable adverse event
- In the Investigator's opinion, the subject is non-compliant with the protocol requirements
- Subject wishes to withdraw consent
- Investigator elects to end the study

d. Adverse event reporting guidelines

Definition of Adverse Events (AEs)

An adverse event (AE) is defined as any untoward medical occurrence in a subject administered a study drug, and which does not necessarily have a causal relationship with this treatment. An AE can therefore be any unfavorable and unintended sign (including an abnormal laboratory finding), symptom, or disease temporally associated with the use of a study drug, whether or not related to the study drug.

An abnormality identified during a medical test (e.g., laboratory parameter, vital sign, ECG data, physical exam) should be defined as an AE only if the abnormality meets one or more of the following criteria:

- Induces clinical signs or symptoms
- Requires active intervention
- Requires interruption or discontinuation of study medication
- The abnormality or investigational value is clinically significant in the opinion of the investigator

Definition of Serious Adverse Events (SAEs)

A serious AE is any untoward medical occurrence that, at any dose:

- Results in death,
- Is life threatening (an event in which the subject is at risk of death at the time of the event; it does not refer to an event which hypothetically might have caused death if it was more severe),
- Results in persistent or significant disability/incapacity,
- Results in congenital anomaly, or birth defect,

- Requires inpatient hospitalization or leads to prolongation of hospitalization (hospitalization for treatment/observation/examination caused by AE is to be considered as serious)
- Other medically important events

Medical and scientific judgment will be exercised in deciding whether expedited reporting is appropriate in other situations, such as important medical events that may not be immediately life-threatening or result in death or hospitalization but may jeopardize the subject or may require intervention to prevent one of the other outcomes listed in the definition above. These events, including those that may result in disability, will be considered serious.

Criteria for Causal Relationship to the Study Drug

Adverse events that fall under either "Possible" or "Probable" should be defined as "adverse events whose relationship to the study drugs could not be ruled out."

Causal relationship	Criteria for causal relationship
to the study drug	
Not Related	A clinical event, including laboratory test abnormality, with a temporal relationship to drug administration which makes a causal relationship improbable, and/or in which other drugs, chemicals or underlying disease provide plausible explanations.
Possible	A clinical event, including laboratory test abnormality, with a reasonable time sequence to administration of the drug, but which could also be explained by concurrent disease or other drugs or chemicals. Information on drug withdrawal may be lacking or unclear.
Probable	A clinical event, including laboratory test abnormality, with a reasonable time sequence to administration of the drug, unlikely to be attributed to concurrent disease or other drugs or chemicals, and which follows a clinically reasonable response on re-administration (re-challenge) or withdrawal (de-challenge).

Criteria for Defining the Severity of an Adverse Event

The following standard with 3 grades is to be used to measure the severity of adverse events, including abnormal clinical laboratory values.

- Mild: No disruption of normal daily activities
- Moderate: Affect normal daily activities
- Severe: Inability to perform daily activities

Reporting of Serious Adverse Events (SAEs)

In the case of a serious adverse event (SAE), the investigator will submit a report through eIRB within 5 working days/7 calendar days of the date the investigator first becomes aware of the problem as per Partners policy.

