- a. higher contrast and spatial resolution of PET/CT for detection of small lesions, which we think will result in improved sensitivity as compared to indium-111 pentetrotide SPECT;
- b. a nearly 75% reduction in the whole body effective radiation dose to patients from a single administration of gallium-68 dotatate (from 16.4 mSv for Octreoscan to 4.3 with Dotatate);
- c. convenience for patients and practical to perform. The entire gallium-68 dotatate PET imaging procedure takes ~2 hours in a single visit, compared to ~24 hours over 2 visits for octreoscan imaging.

II. SPECIFIC AIMS

Aim 1

To investigate if patients with clinically suspected cardiac sarcoidosis exhibit a myocardial OctreoScan or DOTATATE signal high enough (heart-to-blood pool ratio ≥ 2.0) to be visually detected compared to a control group of individuals (expected heart-to-blood pool ratio of ~ 1.0).

Sub-Aim1

To evaluate whether 4-hour (early) compared to 24-hour (delayed) post-OctreoScan injection imaging yields similar lesion detection performance.

Sub-Aim2

To correlate localization and number of increased radiotracer foci between FDG-PET and OctreoScan or between FDG-PET and DOTATATE studies.

Sub-Aim3

To explore the effect of treatment on DOTATATE activity in the heart on follow-up scans

III. SUBJECT SELECTION

We will enroll 30 adult subjects meeting the following inclusion/exclusion criteria.

a. Inclusion Criteria for initial study

- Individuals aged 18 or older

- Documentation of biopsy-proven sarcoidosis OR patients with typical findings on FDG PET and MRI without previous biopsy.

- Clinical suspicion of cardiac involvement defined as the presence of any of the following: high-degree A-V nodal block, complete bundle branch block, reduced left or right ventricular systolic function, any cardiac arrhythmia, and/or unexplained chest pain, dyspnea or syncope

- PET/CT imaging demonstrating abnormal myocardial FDG uptake consistent with active inflammatory myocardium.

b. Exclusion Criteria for initial study

-Initiation of steroids or any other immunosuppressive medication(s) following the completion of FDG-PET, as these medications, in theory, may subsequently suppress OctreoScan or DOTATATE uptake in the heart.

- Patients with history of neuroendocrine tumors (specially insulinomas)
- Patients taking the medication Octreotide
- Patients on total parenteral nutrition (TPN)
- Women who are pregnant or breastfeeding

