Enrolled patients will be prospectively imaged after injection of either the radiotracer Indium-111 Penteotride (OctreoScan) or DOTATATE. We expect imaging 10 patients with OctreoScan and 20 patients with DOTATATE. No one will receive both radiotracer injections.

Patients will be scheduled for imaging Tuesday through Friday (no Mondays), since the dose of OctreoScan and DOTATATE must be requested by noon for next day delivery. Subjects will be advised to remain well hydrated prior to and for at least one day after tracer injection, this to reduce radiation exposure.

Women may participate in this study only if they are certain they are not pregnant. If the subject is a woman of childbearing age, a pregnancy test will be performed before OctreoScan or DOTATATE injection unless she has a history of total hysterectomy, is post-menopausal for more than 2 years or post-tubal ligation for more than 1 year.

OctreoScan Protocol

Visit 1 (Screening)

- Review the study with the subject and obtain written informed consent and HIPAA authorization.
- Assign the subject a unique study number.
- Record demographics data.
- Record medical history, including a history of biopsy-proven systemic sarcoidosis, diagnosis date, and prior treatments.
- Record concomitant medications.
- Schedule subject for Visit 2.

Visit 2 (Study Day 1)

- Subject arrives to the Nuclear Medicine Department.
- Concomitant medications review.
- Perform abbreviated physical examination.
- Perform and record vital signs.
- Place a peripheral intravenous (IV) line.
- Perform STAT quantitative serum hCG testing prior to each administration of Octreoscan
- Administer OctreoScan IV.
- Observe patient for 30 minutes post OctreoScan injection.
- Patient is to have a break and return to the Nuclear Medicine Department in 4 hours.
- Perform first set of images (~90 minutes)
- Subject can leave the Nuclear Medicine Department

[figure not shown]
Visit 3 (Study Day 2)

- Subject returns to the Nuclear Medicine Department 24 hours after OctreoScan injection
- Record any Adverse Experiences.
- Perform second set of images (~90 minutes).
- Subject has completed the study protocol at this point.

Follow Up

• All patients will be contacted by telephone at approximately 36-48 hours following the last scan for AE monitoring.

Figure 3. Example of Study Visits for OctreoScan Protocol

Study Day 1 (Approximately 6 hours)

Study Day 2 (Approximately 2 hours)

24 hours post	Whole Body	SPECT/CT	

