DOTATATE will be given intravenously at the dose of 4.0 mCi (148 MBq). They will then be observed for 60 minutes post DOTATATE injection at the nuclear medicine lab.

Cardiac acquisition: Individuals will be positioned with the help of a CT topogram (grid over the heart, level of the carina), and a low-dose CT scan (120 kVp, 20 - 30 mA) will be acquired for attenuation correction of PET emission data to cover the entire chest. This will be followed by a 20-minute ECG-gated 3-D PET acquisition of the chest and myocardium.

Imaging Processing:

All PET images will be reconstructed with attenuation correction (Matrix 128x128, OSEM, subsets 28, iteration 2, post filter 6.0 mm), and processed and reviewed using the vendor-supplied HERMES software package.

d. Data to be collected and when the data is to be collected

Visit 1. We will collect demographics data, medical history, prior treatments, and concomitant medications, as well as confirm a negative STAT quantitative serum hCG testing prior to the administration of Octreoscan or DOTATATE.

After visit 3 for OctreoScan or after visit 2 for DOTATATE we will analyze and interpret the images as following:

Image Interpretation for OctreoScan:

OctreoScan uptake in the heart will be assessed both qualitative and semi-quantitatively.

1. Qualitative Assessment of OctreoScan cardiac uptake: Two board-certified nuclear medicine physicians will review the early and delayed whole body planar and SPECT/CT images independently of each other and grade each image set based on OctreoScan uptake in the heart as: 1) negative, 2) borderline positive or 3) definitely positive. In this latter case, the number and location (relative to the left ventricular wall position) of positive lesions will be recorded. Similarly, FDG-PET studies (performed as part of the inclusion criteria) will be reviewed and the number and location of FDG-avid lesions recorded.

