2. Semi-quantitative assessment of OctreoScan cardiac uptake: A heart to blood pool background ratio will be calculated using a circular region of interests (ROI) applied to each focus of increased radiotracer uptake visualized in the left ventricle on the transverse and/or coronal tomographic slice of the fused SPECT/CT images. A background ROI of the same size will be applied to the blood pool in the left ventricular cavity. In addition, the relative myocardial contrast will be assessed with measurement of myocardial uptake in ROIs positioned in: 1) interventricular septum 2) lateral wall 3) anterior wall and 4) inferior wall. ROI placement will be confirmed via image fusion with the CT portion from the SPECT/CT study (similar to Figure 2). This qualitative and semiquantitative approach will be performed in both early and delayed datasets by 2 separate nuclear medicine physicians.

Image Interpretation for DOTATATE:

DOTATATE uptake in the heart will be assessed both qualitative and semi-quantitatively.

1. Qualitative Assessment of OctreoScan cardiac uptake: Two board-certified nuclear medicine physicians will review the limited whole body and cardiac PET/CT images independently of each other and grade each image set based on DOTATATE uptake in the heart as: 1) negative, 2) borderline positive or 3) definitely positive. In this latter case, the number and location (relative to the left ventricular wall position) of positive lesions will be recorded.

2. Quantitative assessment of DOTATATE cardiac uptake: The axial PET image slice with maximum cardiac uptake will be selected. A standardized 15 mm circular region will be placed over each myocardial wall area with the peak activity. ROI placement will be confirmed via image fusion with the CT portion from the PET/CT study. Each ROI will be used to derive maximum (SUVmax) and mean standardized uptake values (SUVmean). A background ROI of the same size will be applied to the blood pool in the left ventricular cavity, and similarly, SUVmax and SUVmean will be derived to serve as reference. Then, signal-to-background ratios will be calculated.

This qualitative and semi-quantitative approach will be performed in both early and delayed datasets by 2 separate nuclear medicine physicians.

BIOSTATISTICAL ANALYSIS

a. Specific data variables being collected for the study

Please see excel attachments

b. Study endpoints

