Primary Endpoint: Positive or abnormal OctreoScan or DOTATATE uptake in patients with cardiac sarcoidosis

Secondary Endpoint: Differences in OctreoScan uptake at 4 hours vs. 24 hours post-radiotracer injection

c. Statistical methods

Data Ascertainment and Analysis:

All statistical analysis will be done using SPSS (version 21.0). A P value <0.05 will be considered statistically significant for all calculations.

Qualitative assessment of OctreoScan or DOTATATE cardiac uptake: First, Cohen's kappa coefficient will be used to examine the visual inter-rater agreement between readers. We expect a kappa of at least 0.9 (excellent). Subsequently, the percentage of patients with abnormal OctreoScan or DOTATATE will be compared between patients with suspected sarcoidosis and those in a control group (Table 1, Figure 2) using chi2.

Semiquantitative assessment of OctreoScan or DOTATATE cardiac uptake: The heart-to-blood pool ratio is a unitless continuous variable. We will use paired t-test to compare within group OctreoScan uptake between early and delayed imaging, and independent-measures t test to compare OctreoScan or DOTATATE uptake between patients with suspected sarcoidosis and the control group.

We will also investigate whether delayed imaging may lead to improved lesion detection performance due to a higher/better target-to-background ratio compared to early imaging. We will employ chi2 to compare if percentage of patients with abnormal OctreoScan varies significantly both on a patient- and lesion-basis between early and delayed imaging in both study groups.

Evaluation of early vs. delay imaging: We will employ chi2 to compare if percentage of patients with abnormal OctreoScan varies significantly both on a patient- as well as lesion-basis between early and delayed imaging in both study groups.

Comparison with FDG-PET: We will also compare if foci of increased OctreoScan or DOTATATE uptake are similar in number and localization compared to FDG-PET scans.

Expected Results:

Our main hypothesis is that OctreoScan or DOTATATE uptake in the heart will be semiquantitatively (heart-to blood pool ratio will be ≥ 2.0) high enough to allow visualization of OctreoScan or DOTATATE activity in patients with cardiac sarcoidosis, compared to the control group, where myocardial uptake will be similar to blood pool activity (heart-to blood pool ratio of ~ 1.0).

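### Sub-Aim 2 says 'correlate', the methods say 'similar', and no statistic is named; if foci counts are correlated, the result cannot show similarity to FDG-PET

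*Combined protocol and SAP*

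**What the plan says.** Section II, Sub-Aim2, states the objective: "To correlate localization and number of increased radiotracer foci between FDG-PET and OctreoScan or between FDG-PET and DOTATATE studies".

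Under Biostatistical Analysis, c. Statistical methods, the paragraph on comparison with FDG-PET says: "We will also compare if foci of increased OctreoScan or DOTATATE uptake are similar in number and localization compared to FDG-PET scans". It gives no test, coefficient, agreement measure, margin, unit of analysis or rule for matching sites. The only general decision rule is "A P value <0.05 will be considered statistically significant for all calculations". Other paragraphs of that section do name techniques: kappa between readers, chi-square for percentages, and t-tests for uptake ratios.

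Every patient enters with an abnormal FDG scan (section III.a: "PET/CT imaging demonstrating abnormal myocardial FDG uptake consistent with active inflammatory myocardium"). The total is 30, and section V.a splits it by tracer: "We expect imaging 10 patients with OctreoScan and 20 patients with DOTATATE".

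Section V.d, on image interpretation, has the readers grade each tracer scan as negative, borderline positive or definitely positive. Only the last grade leads to a lesion count: "In this latter case, the number and location (relative to the left ventricular wall position) of positive lesions will be recorded". For FDG-PET, the OctreoScan paragraph asks to have "the number and location of FDG-avid lesions recorded".

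**The concern.** The methods pose a question of agreement: does the tracer show about as many foci as FDG-PET, in the same places? The one operation the plan attaches to foci counts is to correlate them. A correlation P value is computed under the hypothesis that the two counts are unrelated across patients. Patients with more FDG foci will tend to have more tracer foci even when the tracer loses a fixed fraction of them. The coefficient therefore does not reveal the failure that matters most for a tracer judged against FDG-PET.

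Sub-Aim 2 is also the only planned analysis that could reveal partial loss of FDG-defined disease within a patient. The other FDG hypothesis, under Expected Results, concerns the number of abnormal patients. A patient with one of four foci detected still counts as abnormal there.

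**Working it through.** **Plan's own figure.** There is none to reproduce. The documents give no expected correlation, margin, power or foci counts for this aim.

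**Inputs from the documents.** n = 10 (OctreoScan) and n = 20 (DOTATATE), section V.a; P<0.05, Statistical methods (taken as two-sided, since sidedness is not stated); all patients FDG-abnormal, section III.a (taken as at least one FDG focus each).

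**Assumptions.** The distribution of FDG foci per patient, with mean M and variance V, is assumed over a range. The tracer sees each FDG focus independently with probability q = 0.5 and adds no false foci.

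**Step 1: correlation implied by losing half the foci.** With N FDG foci and T ~ Binomial(N, q), Cov(N,T) = qV and Var(T) = q²V + q(1−q)M. Hence r = √[qV / (qV + (1−q)M)], which at q = 0.5 is r = √[V/(V+M)]. For counts uniform on 1–4, M = 2.5 and V = 1.25, so r = √(1.25/3.75) = 0.58. If exactly half were missed in every patient, r would be 1.

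**Step 2: chance of significance.** The critical |r| is 0.632 at n = 10 and 0.444 at n = 20. The table gives the share of 20,000 simulated trials with a significant positive Pearson correlation.

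| Assumed FDG foci per patient | M | V | r | n = 10 | n = 20 |
|---|---|---|---|---|---|
| 1 or 2 (70%, 30%) | 1.30 | 0.21 | 0.37 | 20% | 38% |
| 1, 2 or 3 (60%, 30%, 10%) | 1.50 | 0.45 | 0.48 | 31% | 58% |
| Uniform 1–4 | 2.50 | 1.25 | 0.58 | 45% | 82% |
| Zero-truncated Poisson | 2.31 | 1.59 | 0.64 | 54% | 86% |
| Uniform 1–6 | 3.50 | 2.92 | 0.67 | 65% | 95% |

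A separate run of 1,500 trials gave 37% for the 1-or-2 case at n = 20. Larger or more dispersed counts go beyond these ranges: a truncated Poisson with mean 5 gives 69% and 95%, and a geometric distribution with mean 3 gives 81% and 98%. Spearman rates are up to about 12 points lower.

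**Step 3: misses that cluster by patient.** If detection varies uniformly from 0 to 1 between patients, the rates are 28–58% at n = 10 and 49–84% at n = 20. If the tracer misses every focus in half the patients, they are 18–38% and 36–56%.

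**Step 4: a paired analysis of the same data.** In the Step 2 simulations, a paired t-test on the count difference detects the shortfall in 87–100% of trials at n = 10 and about 100% at n = 20. For uniform 1–4, the mean of tracer minus FDG is 1.25 − 2.5 = −1.25. The variance of the difference is 0.25V + 0.25M = 0.9375, so SD = 0.97. Expected results are then:
- 95% interval at n = 20: −1.25 ± 2.093 × 0.97/√20, about −1.70 to −0.80.
- 95% interval at n = 10: −1.25 ± 2.262 × 0.97/√10, about −1.94 to −0.56.
- Limits of agreement: −1.25 ± 1.96 × 0.97, about −3.15 to 0.65.

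**Step 5: precision of the share detected.** Under the same assumption there are about 20 × 2.5 = 50 FDG foci in the DOTATATE patients, giving 0.50 ± 1.96√(0.25/50), or 0.36 to 0.64. With 10 × 2.5 = 25 foci in the OctreoScan patients the interval is 0.30 to 0.70. Both widen if misses cluster within patients.

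**The case against.** The strongest reply is that the plan specifies no correlation test. The aim uses the word 'correlate', but the methods paragraph says 'compare' and no coefficient appears anywhere. Location by ventricular wall has no obvious Pearson or Spearman form, so 'correlate' may simply mean matching findings between two scans. This stands, and it is why the point is conditional. It does not remove the point: on the looser reading, the comparison has no method at all.

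A reader might also infer that a significant correlation would be reported as proof of similarity. No section says so. The blanket P<0.05 sets a threshold and does not define this inference.

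A reader might set the rates above against a nominal 5% and call them an inflated error rate. That would be wrong. In these scenarios the counts really are associated, so rejecting no association is correct and the rates are power. The trouble is that the hypothesis tested is not the one of interest.

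Finally, this is a sub-aim of a 30-patient pilot and is neither the primary nor the secondary endpoint. Since all patients are FDG-abnormal, the planned percentage with abnormal tracer uptake already reveals whole-patient misses. That is fair, and it limits the weight of the point, but that percentage does not show partial loss within a patient.

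**Conclusion.** The point holds in conditional form. The aim and the methods use different words for the FDG comparison, neither gives an agreement measure, and the one operation named for counts cannot answer the question posed. That a correlation is blind to a proportional shortfall follows from the algebra and needs no assumption about counts.

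The size does rest on assumptions: foci distributions the documents do not give, independent misses and no false foci. With half the foci missed and up to six FDG foci per patient, significance would occur in about 38–95% of trials at n = 20 and 20–65% at n = 10. It would be tempting to say that such a tracer would usually pass. That is not supported for the 10 OctreoScan patients in most scenarios. At n = 20 it also fails when FDG counts barely vary (38% with one or two foci) or when the tracer misses all foci in half the patients (36–56%).

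The plan should be corrected before analysis; the primary endpoint is not affected.

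**What to change.** 1. In Sub-Aim2, replace 'correlate' with 'assess agreement in'. In Statistical methods, state that no correlation P value will be used as evidence of similarity. A coefficient may be shown descriptively.
2. For each tracer separately, report the per-patient difference in number of foci (tracer minus FDG) with its mean, 95% confidence interval and limits of agreement.
3. For each tracer separately, report the share of FDG foci also seen on the tracer, matched by ventricular wall position, with a confidence interval obtained by resampling patients.
4. In section V.d, record a foci count for every scan: 0 for negative scans and a stated count for borderline ones. State how the two readers' counts are combined. Without these rules the difference cannot be computed unambiguously, because tracer foci are now recorded only for 'definitely positive' scans. Repeat the FDG lesion-recording instruction under DOTATATE, since it appears only under OctreoScan.

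The cost is a few sentences in the aim, the methods and the reading instructions, plus a count entered for borderline scans. No extra scans, readers or patients are needed. The downside is wide intervals at n = 10 and n = 20, which will look less favourable than a small correlation P value.

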However, to date no studies have systematically evaluated the level of uptake of somatostatin receptor ligands in the heart under baseline conditions, which is necessary before investigating any pathologic accumulation.

[figure not shown]

Figure 1.

Please notice the low-level OctreoScan cardiac uptake (red arrows) similar to blood pool of subject A, contrasting with the diffuse intense uptake of FDG in the entire heart (blue arrows) of subject B despite prolonged fasting and dietary modifications in an attempt to suppress physiologic FDG myocardial uptake. None of these subjects have history of sarcoidosis.

Table 1	T-BP	SD	Min	Max	P value
Organ (n = 15)	Ratio	30	IVIIII	IVIAA	r value
Septum	1.02	0.15	0.79	1.33	
Inferior wall	1.03	0.13	0.86	1.32	0.0004
Lateral wall	0.92	0.15	0.69	1.15	0.0004
Anterior wall	0.81	0.15	0.65	1.09	
Total LV	0.94	0.17			
Lung, right	0.28	0.14	0.11	0.57	0.32
Lung, left	0.30	0.11	0.15	0.49	0.52
Total lung	0.29	0.12			
Liver, right lobe	5.51	1.94	2.76	8.17	0.33
Liver, left lobe	5.73	2.57	2.55	11.61	0.33
Total Liver	5.69	2.21			
Kidney, right	36	22	14	92	0.38
Kidney, left	36	19	13	75	0.38
Total Kidney	36	21			
Spleen	27	11	10	50	n/a

[figure not shown]

Figure 2. For this reason we studied 15 consecutive adult

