patients (7 men and 8 women, mean age 62 years) who underwent OctreoScan with SPECT/CT of the chest for a clinical indication between the periods of April and November of 2013 at the University of Washington in Seattle. Most common clinical indication was detection of local and/or metastatic neuroendocrine tumors. Patients were injected with ~ 6 mCi of OctreoScan, and SPECT/CT of the chest was acquired 24 hr post-injection. OctreoScan uptake was semiquantitatively calculated using a target to blood pool ratio approach. Figure 2 depicts fused SPECT/CT images of how this was performed. Circular region of interests (ROI) of ~20 mm diameter were applied to left ventricular (LV) cavity blood pool (used as background, 2A and 2D), LV anterior (2B), inferior (2C), lateral wall (2E) and septum (2F), as well as the lungs (not shown), liver (2G), spleen (2G) and kidneys (2H). Results: Visually, the myocardium exhibited indistinguishable activity compared to the LV blood pool. However, there was significant LV regional differences in the uptake ratio/index as shown in **Table 1**. The inferior wall and septum showed higher (above blood pool) and the lateral and anterior walls lower (below blood pool) uptake ratios. This is most likely due to scatter emitted from the liver and spleen (Fig 2G) into the inferior wall (Fig 2C) and, to a lesser extent, the inferior portion of the septum. Likewise, identification of the septal wall (Fig 2F) was difficult given the lack of enough contrast definition on SPECT and CT images, for which an anatomical assumption was made, which makes ROI-based estimates less accurate at this location. These data demonstrated that under baseline conditions. OctreoScan uptake in the heart is indistinguishable from LV blood pool (~ 0.94 ± 0.17). These findings provide solid empirical basis for the work proposed in this project; the hypotheses are mechanistically plausible, clinically important, and testable.

d. Differences between OctreoScan and DOTATATE

There are important biological, technical, and practical differences between these radiopharmaceuticals that deserve a brief mention. Like indium-111 pentetrotide (Octreoscan®), 68-gallium dotatate has similar affinity for the same group of somatostatin receptors in inflammatory leukocytes (preferentially somatostatin receptor 2). The availability of 68-gallium dotatate provides several advantages, which are highly beneficial to the patients in this pilot study, including:

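### Readers are made independent only of each other: no masking to FDG, group or time point is stated, and the controls have no planned re-read, so visual positivity and the FDG match may be biased upward

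*Combined protocol and SAP*

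**What the plan says.** Section III.a makes FDG positivity a condition of entry: "PET/CT imaging demonstrating abnormal myocardial FDG uptake consistent with active inflammatory myocardium".

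Section V.d describes the reading. For OctreoScan, two nuclear medicine physicians "will review the early and delayed whole body planar and SPECT/CT images independently of each other" and give each image set one of three grades, the middle one being borderline. The same paragraph continues: "Similarly, FDG-PET studies (performed as part of the inclusion criteria) will be reviewed and the number and location of FDG-avid lesions recorded". For DOTATATE, two physicians "will review the limited whole body and cardiac PET/CT images independently of each other", using the same three grades. The DOTATATE text has no FDG step of its own, but the FDG comparison in the Biostatistical Analysis section (part c) covers both tracers.

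That section sets the primary endpoint as positive or abnormal tracer uptake. The percentage of patients with abnormal uptake is compared "between patients with suspected sarcoidosis and those in a control group (Table 1, Figure 2) using chi2". Those controls are the series introduced in section I.c with the words "For this reason we studied 15 consecutive adult": patients who had a clinical OctreoScan in 2013 at another institution. Their visual result is already given: "Visually, the myocardium exhibited indistinguishable activity compared to the LV blood pool".

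**The concern.** Two readers who do not confer can still share the same outside information. Here that information is strong. Anyone who knows that a scan is a study patient's scan can infer that the patient's FDG study was abnormal, and nothing in the plan keeps the FDG images or lesion map away from the person grading the tracer scan. Expectation would then push doubtful calls towards positive, and towards the walls where FDG was positive. It would do so in patients only, because the controls were assessed outside this process.

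Three results depend on these calls: the chi-square comparison of patients with controls, the number and location match with FDG (Sub-Aim 2), and the hypothesis under Expected Results that the tracer finds about as many abnormal patients as FDG does. A positive initial DOTATATE scan is also the entry condition for the follow-up study (section III.c), so over-calls could carry into Sub-Aim 3. The planned kappa gives no protection, since two readers with the same expectation can agree closely and both be wrong.

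**Working it through.** The plan gives no sample size calculation, power or bias figure on this point, so there is nothing to reproduce. The check is mainly a comparison of the text for the two groups.

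| Feature | Patients | Controls |
|---|---|---|
| FDG status | All abnormal (III.a) | Not described |
| Tracer | OctreoScan, 10 expected; DOTATATE, 20 expected (V.a) | OctreoScan only, n = 15 (I.c) |
| Imaging time | OctreoScan at 4 h and 24 h; DOTATATE after 60 min | 24 h |
| Visual read | Two readers, three grades (V.d) | One reported summary; readers and scale not given |
| Masking or reading order | None stated | None stated; no re-read planned |

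**Link between positivity and FDG agreement.** All n patients are FDG-positive. If r of them are tracer-positive, patient-level agreement with FDG is r/n, which is also the positivity rate. Each over-called patient therefore raises both figures by 1/n: 10 percentage points at n = 10 and 5 at n = 20. The two results are not independent support for each other.

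**How few positive calls give significance (illustration).** Assumption: the reported control result means 0 of 15 positive. For r of n patients against 0 of 15, uncorrected chi-square is (n + 15)(15r)² / [n × 15 × r × (n − r + 15)].

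- n = 10, r = 3: 25 × 45² / (10 × 15 × 3 × 22) = 5.11, p = 0.024
- n = 20, r = 5: 35 × 75² / (20 × 15 × 5 × 30) = 4.38, p = 0.037
- n = 30, r = 7: 45 × 105² / (30 × 15 × 7 × 38) = 4.14, p = 0.042

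One positive patient fewer gives 3.26, 3.39 and 3.46, all below the 3.84 needed. Fisher's exact test needs 4 of 10, 6 of 20 or 8 of 30.

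**Effect of an assumed over-call (illustration).** Suppose there is no true signal, and patients alone are over-called by a fixed number of percentage points above the control call rate. The chance that uncorrected chi-square falls below p = 0.05, by exact binomial enumeration against 15 controls, is:

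| Control call rate | Over-call (points) | n = 10 | n = 20 | n = 30 |
|---|---|---|---|---|
| 0% | 10 | 7% | 4% | 3% |
| 0% | 20 | 32% | 37% | 39% |
| 0% | 30 | 62% | 76% | 84% |
| 5% | 10 | 10% | 9% | 8% |
| 5% | 20 | 31% | 36% | 38% |
| 5% | 30 | 56% | 66% | 70% |

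Both the over-call and the control call rates are assumptions. The table shows how sensitive the test is. It does not estimate the bias.

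**Ratio analysis.** The OctreoScan text in V.d places ROIs on each focus the reader sees, and also on the septum, lateral, anterior and inferior walls. The control series used the same four walls. The focus-based ratios inherit the reader's choice of focus; the fixed-wall ratios depend much less on it. DOTATATE ROIs follow peak activity, not a positive call.

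**The case against.** The strongest reply is that the plan is silent on masking and does not prescribe unmasked reading. That is right, and it limits what can be claimed. A reader might infer any of the following, none of which the documents state:

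- **That the tracer readers know each FDG result and record the FDG lesions themselves.** The FDG sentence is in the passive and names neither reader nor order. Knowledge of FDG status is an inference from the entry criterion and the absence of masking.
- **That the 4 h and 24 h sets are read side by side.** Each image set receives its own grade. Interpretation after visit 3 means only that both sets are available by then.
- **That the primary endpoint is purely the visual grade.** It is worded as positive or abnormal uptake and is not tied to the three-level scale. Aim 1 uses a heart-to-blood-pool ratio of at least 2.0.
- **That the controls were graded without the three-level scale.** Their scale and readers are not described. What can be said is that no re-read is planned.

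It is also fair to say that this is a single-centre pilot, that FDG concordance is a sub-aim with no named test, and that an over-call of 10 points leaves the rejection rate between 3% and 10% in the table. Nor can masking do everything: enrolled patients remain known to be FDG-positive, and site differences may give the controls away.

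What stands is the gap itself. A significance test is planned on grades obtained by different processes in the two groups, and nothing separates the tracer reading from the FDG reading.

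**Conclusion.** The concern holds as a risk of bias that the plan leaves open. It does not show that bias will occur. Visual positivity in patients and the FDG lesion match may be biased upward, because FDG positivity is built into enrolment, no masking or reading order is stated, and the controls are an external series already reported. The expected direction follows from these facts; the size cannot be derived from the documents. With 0 of 15 positive controls assumed, 3 of 10, 5 of 20 or 7 of 30 positive patients suffice for significance, so a few doubtful calls could matter. No direction is claimed for the 4 h versus 24 h comparison. The fixed-wall OctreoScan ratios are less exposed and should not be dismissed on this ground.

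**What to change.** Add a short reading procedure to section V.d, using the same two readers:

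1. Grade and lock all OctreoScan and DOTATATE reads and lesion maps before, and without access to, FDG images or reports. Read FDG in a later session, then match lesions.
2. Present the 4 h and 24 h OctreoScan sets as separate, unlabelled cases.
3. If the control images can be obtained, de-identify the 15 control 24 h chest SPECT/CT studies, mix them in random order with the patients' 24 h OctreoScan chest SPECT/CT, and grade them on the same three-level scale.
4. Report the DOTATATE-versus-control visual comparison as descriptive, because the control series contains no DOTATATE scans.

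Step 1 covers both tracers and needs only a reading order and a later FDG session. Step 2 adds some case handling. Step 3 adds 15 scans per reader and an image transfer; the documents do not show that the images are available. It can serve only the 24 h OctreoScan reads (about 10 of the 30 patients), because no 4 h controls exist either. No extra reader is needed. The remaining limits, that enrolment itself reveals FDG status and that site differences may partly unmask the controls, should be stated when the results are reported.
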